4. TAKING YOUR CHILD TO THE DENTIST

4a. The following questions are about taking your child to the dentist for any reason. Please circle the number that best fits your response.

	Strongly Disagree	Disagree	Neither disagree nor agree	Agree	Strongly Agree
4a1. I want to take my child to the dentist.	1	2	3	4	5
4a2. I plan to take my child to the dentist.	1	2	3	4	5

Study Site _____ ID# _____

Caregiver Questionnaire-Baseline

4b. The following questions are about how you would feel about taking your child to the dentist for preventive care (checkups, cleanings, topical fluoride) and dental treatments (fixing cavities). Please tell us how you feel by circling the number that best fits your response.

My feelings about the dentist will get in the way of taking my child to the dentist for...	Strongly Disagree	Disagree	Neutral	Agree	Strongly Agree
4b1. preventive care.	1	2	3	4	5
4b2. dental treatments.	1	2	3	4	5

4c.– 4d. The following questions are about what others think about taking your child to the dentist for preventive care and dental treatments. Please tell us how you feel by circling the number that best fits your response.

People important to me ...	Strongly Disagree	Disagree	Neutral	Agree	Strongly Agree
4c1. think that I should take my child to the dentist at least once a year.	1	2	3	4	5
4c2. would approve if I were to take my child to the dentist at least once a year.	1	2	3	4	5
4c3. take their child to the dentist at least once a year.	1	2	3	4	5
4d1. think that I should take my child to the dentist when a tooth problem is found.	1	2	3	4	5
4d2. would approve if I were to take my child to the dentist when a tooth problem is found.	1	2	3	4	5
4d3. take their child to the dentist when a tooth problem is found.	1	2	3	4	5

Study Site _____ ID# _____

Caregiver Questionnaire-Baseline

4e. Sometimes parents delay their child's dental care when other things get in the way. How likely are you to take your child to the dentist when the following happen to you? Please circle the number that best fits your response.

How likely are you to take your child to the dentist when you are ...	Very Likely	Moderately Likely	Somewhat Likely	Not At All Likely
4e1. under a lot of stress	1	2	3	4
4e2. depressed	1	2	3	4
4e3. anxious	1	2	3	4
4e4. feeling like you do not have the time (too busy)	1	2	3	4
4e5. tired	1	2	3	4
4e6. worrying about other things in your life	1	2	3	4

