32d. Diet or eating habits can cause cavities in a child	1	2	3	4	5
32e. Chance or bad luck can cause cavities in a child	1	2	3	4	5
32f. Poor dental care can cause cavities in a child	1	2	3	4	5
32g. Something a parent/caregiver does can cause cavities in a child	1	2	3	4	5
32h. A parent/caregiver's negative thoughts can cause cavities in a child	1	2	3	4	5
32i. Family problems or a parent/caregiver's worries can cause cavities in a child	1	2	3	4	5
32j. A parent/caregiver's feelings (feeling down, anxious) can cause cavities in a child	1	2	3	4	5
32k. A child's lack of ability to fight off infections can cause cavities	1	2	3	4	5

Site: _____ ID#_____

33. Please list in order the three most important things that you believe cause cavities in children. You may use any of the items from the previous question or you may have other ideas of your own.

[figure not shown]
The most important causes for me are:

1st _____

2nd _____

3rd _____

Family Access to Dentist Study

Study Site: _____ ID#: _____

Caregiver Questionnaire-2-week Follow-up

1. TAKING YOUR CHILD TO THE DENTIST**1.1 Did your child visit the dentist after the school dental screening?**

- a) Yes → Please GO TO Question 1.2
- b) No, but I have made an appointment with the dentist → Please SKIP TO Question 1.5
- c) No, and I have not made an appointment with the dentist → Please SKIP TO Question 1.6

If you answered YES to Question 1.1 above, please answer the following questions:

1.2 What is the name of the dental clinic / dentist where you took your child?

1.3 Did you take the referral letter (from the school dental screening) with you to the dentist?

- a) Yes
- b) No

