1.4 Did your child complete the needed dental treatment?

- a) Yes

If YES, how many visits were needed to complete your child's dental treatment? _____

- b) No, but my child has a follow-up appointment

If NO, when is the follow-up appointment? _____

- c) No

If NO, why did your child not complete dental treatment? _____

- d) Don't know

Please GO TO Question 1.5

Study Site: _____ ID#: _____

Caregiver Questionnaire-2-week Follow-up

If you answered YES or NO, but I have made an appointment to Question 1.1 above, please answer the following question:

1.5 Were there any items below that helped you decide to take your child to the dentist/make an appointment with the dentist?

Please circle all that apply.

- a) The referral letter
- b) Information on myths and facts of children's dental health
- c) Helpful hints on getting my child dental care
- d) Information on making a dental appointment for my child
- e) Knowing about the dentists in my area
- f) The outreach individual at my child's school
- g) Don't know

THANK YOU!

Study Site: _____ ID#: _____

Caregiver Questionnaire-2-week Follow-up

If you answered NO, and I have not made an appointment to Question 1.1 above, please answer the following questions:

1.6. The following questions are about taking your child to the dentist.

Please circle the number that best fits your response.

	Strongly Disagree	Disagree	Neither disagree nor agree	Agree	Strongly Agree
1.6a I want to take my child to the dentist.	1	2	3	4	5
1.6b I plan to take my child to the dentist.	1	2	3	4	5

1.7. Why has your child NOT been able to visit the dentist since the school dental screening? Here are some common reasons from other parents – *please circle all that apply*.

- a) The cost is too much.
- b) My child does not have dental insurance or Medicaid.
- c) My family has a problem with our health care plan.
- d) I cannot find a dentist who accepts my child's insurance.
- e) There are no available dentists in my area / I have transportation problems.
- f) It is difficult to get convenient appointment times / My child could not get an appointment.
- g) The dentist did not know how to treat or provide care for my child.
- h) I was dissatisfied with the dentist.
- i) I did not know where to take my child for treatment.
- j) My child refused to go.
- k) My child's treatment is ongoing.
- l) Other, please specify _____

THANK YOU!

Site: _____ ID#: _____

Family Access to Dentist Study

**Your Feelings

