4.5 Did your child visit the dentist after the school dental screening?

- a) Yes → Go to Question 5A
- b) No → Go to Question 5B

Study Site: _____ ID#: _____

Caregiver Questionnaire-Final Follow-up

5A. YOUR THOUGHTS ABOUT THE STUDY

If you answered YES to Question 4.5 (your child visited the dentist), please answer the following questions:

5.1. What is the name of the dental clinic / dentist where you took your child?

5.2. What month after the dental screening did you take your child to the dentist?

5.3. Did you take the referral letter (from the school dental screening) with you to the dentist?

- a) Yes
- b) No

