5.7 Which study group do you think you and your child were in?

- a) Standard letter
- b) Improved letter
- c) Improved letter with materials
- d) Don't know

THANK YOU!

Study Site: _____ ID#: _____

Caregiver Questionnaire-Final Follow-up

5B. YOUR THOUGHTS ABOUT THE STUDY

*If you answered **NO** to Question 4.5 (your child did not visit the dentist), please answer the following questions:*

5.1. The following questions are about taking your child to the dentist. Please circle the number that best fits your response.

	Strongly Disagree	Disagree	Neither disagree nor agree	Agree	Strongly Agree
5.1a I want to take my child to the dentist.	1	2	3	4	5
5.1b I plan to take my child to the dentist.	1	2	3	4	5

5.2. Why has your child NOT been able to visit the dentist since the school dental screening? Here are some common reasons from other parents — please circle all that apply.

- a) The cost is too much.
- b) My child does not have dental insurance or Medicaid.
- c) My family has a problem with our health care plan.
- d) I cannot find a dentist who accepts my child's insurance.
- e) There are no available dentists in my area / I have transportation problems.
- f) It is difficult to get convenient appointment times / My child could not get an appointment.
- g) The dentist did not know how to treat or provide care for my child.
- h) I was dissatisfied with the dentist.
- i) I did not know where to take my child for treatment.
- j) My child refused to go.
- k) My child's treatment is ongoing.
- l) Other, please specify _____

Study Site: _____ ID#: _____

Caregiver Questionnaire-Final Follow-up

5.3 Were there any items below that would have helped you get your child to the dentist?*Please circle all that apply.*

- a) The referral letter
- b) Information on myths and facts of children's dental health
- c) Helpful hints on getting my child dental care
- d) Information on making a dental appointment for my child
- e) Knowing about the dentists in my area
- f) The outreach individual at my child's school
- g) Don't know

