1. LLEVANDO A SU NIÑO/A AL DENTISTA

1.1 ¿Después de la evaluación visual en la escuela, visito su niño/a al dentista?

- a) Si → Por favor VAYA A la Pregunta 1.2
- b) No, pero hice una cita con el dentista → Por favor SÁLTASE a la Pregunta 1.5
- c) No, y no he hecho la cita con el dentista → Por favor SÁLTASE a la Pregunta 1.6

Si contestó SI a la Pregunta 1.1 de arriba, por favor responda a las siguientes preguntas:

1.2 ¿Cuál es el nombre de la clínica dental/dentista donde usted llevó a su niño/a?

1.3 ¿Llevó la carta de referencia (de la evaluación visual dental de la escuela) con usted al dentista?

- a) Si
- b) No

1.4 ¿Completo su niño/a el tratamiento dental que necesitaba?

- a) Si

Si es SI, ¿cuántas visitas fueron necesarias para completar el tratamiento dental de su niño/a? _____

- b) No, pero tiene una cita de seguimiento

Si NO, ¿Cuando está programada la cita de seguimiento? _____

- c) No

Si NO, ¿Por qué su niño/a no completo el tratamiento dental? _____

- d) Don't know

Por favor VAYA a la Pregunta 1.5

2

Sitio del estudio _____ # de identificación _____

2-Semanas Seguimiento

Si usted contestó SI o NO, pero he hecho una cita a la Pregunta 1.1 de arriba, por favor responda a la siguiente pregunta:

1.5 ¿Había alguna articulo abajo que le ayudo a decidir a llevar a su niño/a al dentista ó hacer una cita con el dentista?

Por favor circule todos los que apliquen.

- a) La carta de referencia
- b) Información de mitos y hechos de la salud dental de los niños/as
- c) Consejos útiles para el cuidado dental de su niño/a
- d) Información en hacer citas dentales para su niño/a
- e) Conocer acerca de los dentistas en su área
- f) El alcance individual en la escuela del niño/a
- g) No se

¡Gracias!

Sitio del estudio _____ # de identificación _____

2-Semana Seguimiento

Si contestó NO, y no he hecho una cita a la Pregunta 1.1 de arriba, por favor responda a las siguientes preguntas:

1.6 Las siguientes preguntas son acerca de llevar a su niño/a al dentista.

Por favor circule el número que mejor se adapte a su respuesta

	Completeme nte en desacuerdo	Desacuerdo	Neutral	De acuerdo	Totalmente de acuerdo
1.6a Yo quiero llevar a mi niño al dentista	1	2	3	4	5
1.6b Yo planeo llevar a mi niño al dentista	1	2	3	4	5

1.7 ¿Porque su niño NO ha podido visitar al dentista desde la evaluación dental en la escuela? Aquí hay algunas razones comunes de otros padres por favor circule todas las que apliquen.

- a) Cuesta mucho

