- i) No se

4.2 ¿Desde el inicio del año escolar, tuvo su niño/a algún tipo de cobertura dental? Tal como plan privado, plan preferencial (como una membresía de organización de mantenimiento de salud (HMO por sus siglas en Ingles) o plan de gobierno (como Medicaid).

- a) Si → Por favor responda la pregunta 4.2a
- b) No
- c) No se

4.2a ¿Estuvo su niño/a asegurado por Medicaid o el programa de seguro de salud de niños/as (S-CHIP por sus siglas en Ingles)?

- a) Si
- b) No
- c) No se

4.3 ¿Hay un lugar al que su niño/a usualmente va cuando necesita tratamiento para su problemas dental, como caries o dolor de dientes?

- a) Si → Por favor responda la pregunta 4.3a
- b) No
- c) No se

Sitio del estudio: _____ # de identificación: _____

Cuestionario del cuidador Último seguimiento

4.3a Si su respuesta es SI, es este un lugar:

- a) Oficina del dentista
- b) Departamento de emergencia
- c) Hospital
- d) Clínica
- e) Otro, por favor escriba aquí _____

4.4 Algunas veces personas tienen problemas en obtener todo el tratamiento dental que necesitan. Desde el inicio del año escolar, ¿hubo alguna vez que su niño/a necesito cuidado dental pero fue retrasado o no lo recibió?

a) Si → Por favor responda la pregunta 4.4a

b) No

c) No se

Por favor sáltense la pregunta 4.5

4.4a Despues que un problema fue encontrado por un proveedor dental, ¿qué tipo de tratamiento fue atrasado o no fue recibido? Por favor haga un círculo en todas las que apliquen.

- a) Rellenos
- b) Extracciones (sacarse un diente)
- c) Corona (casquillo de metal)
- d) Terapia de pulpa (endodoncia en diente de leche)
- e) Enfermedad en las encillas
- f) Otro, por favor especifique
- g) No me acuerdo

4.5 ¿Visitó su niño/a al dentista después de la evaluación dental en la escuela?

a) Si → Vaya a la pregunta 5A

b) No → Vaya a la pregunta 5B

5A. SUS PENSAMIENTOS ACERCA DEL ESTUDIO

Si usted contestó SI a la Pregunta 4.5 (su niño visitó al dentista), por favor responda a las siguientes preguntas:

5.1 ¿Cuál es el nombre de la clínica dental/dentista donde usted llevó a su niño/a?

5.2 ¿Qué mes después de la evaluación dental llevo a su niño/a al dentista?

5.3 ¿Llevó la carta de referencia (de la evaluación visual dental de la escuela) con usted al dentista?

- a) Si
- b) No

5.4 ¿Completo su niño/a el tratamiento dental necesario?

- a) Si

Si es SI, ¿cuántas visitas fueron necesarias para completar el tratamiento dental de su niño/a?

- b) No, pero mi niño/a tiene una cita de seguimiento

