Si NO, ¿cuándo es la cita de seguimiento? _____

- c) No

Si NO, ¿porque su niño/a no completo el tratamiento dental? _____

- d) No se

Por favor VAYA a la Pregunta 5.5

Sitio del estudio: _____ # de identificación: _____

Cuestionario del cuidador Último seguimiento

5.5 ¿Hubieron algunos puntos anteriormente que le ayudaron a usted a llevar a su niño al dentista?*Por favor circule todos los que apliquen.*

- a) La carta de referencia
- b) Información acerca de mitos y hechos acerca de la salud dental de los niños/as
- c) Consejos útiles para obtener cuidado dental para su niño/a
- d) Información en cómo hacer una cita dental para su niño/a
- e) Conocer acerca de los dentistas en su área
- f) El alcance individual
- g) No se

5.6 ¿Encontró que la carta de referencia fue fácil de entender?

- a) Si
- b) No

5.7 ¿En cuál grupo de estudio piensa usted que estuvo usted y su niño?

- a) En la carta estándar
- b) En la carta de mejoramiento
- c) En la carta de mejoramiento con materiales
- d) No se

¡GRACIAS!

Sitio del estudio: _____ # de identificación: _____

Cuestionario del cuidador Ultimo seguimiento

5.B SUS PENSAMIENTOS ACERCA DEL ESTUDIO

*Si usted contestó **NO** a la Pregunta 4.5 (su niño/a no visitó al dentista), por favor responda a las siguientes preguntas:*

5.1 Las siguientes preguntas son acerca de llevar a su niño/a al dentista. Por favor circule el número que es más apropiado para su respuesta

	Completamente en desacuerdo	Desacuerdo	Neutral	De acuerdo	Totalmente de acuerdo
5.1a Yo quiero llevar a mi niño/a al dentista	1	2	3	4	5
5.1b Yo planeo llevar a mi niño/a al dentista	1	2	3	4	5

5.2 Porque su niño/a NO ha podido ir a visitar al dentista desde la evaluación visual en la escuela? Aquí hay algunas razones de otros padres – por favor circule todas las que aplican.

- a) Cuesta mucho
- b) Mi niño no tiene seguro dental o Medicaid
- c) Mi familia tiene problemas con nuestro plan de cuidado de salud
- d) No puedo encontrar un dentista que acepte el seguro de mi niño/a
- e) No hay dentistas disponibles en mi área / tengo problema de transporte
- f) Es difícil poder obtener horarios convenientes para las citas / mi niño/a no puede obtener una cita
- g) El dentista no sabe cómo tratar o proveer cuidado a mi niño/a
- h) Yo estaba insatisfecho con el dentista
- i) No sabía a dónde llevar a mi niño/a para tratamiento
- j) Mi niño/a rehúsa a ir
- k) El tratamiento de mi niño/a es continuo (se está llevando a cabo)

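### Follow-up intention is asked only of caregivers who have not acted, so the planned arm comparison of this secondary outcome is not a randomised comparison

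*Combined protocol and SAP*

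**What the plan says.** Section 3.2.2 defines behavioural intention as the sum of two five-point items (want to, and plan to, take the child to the dentist). It calculates change between baseline, 2 weeks and final follow-up, and Table 3.2.1 lists all three times.

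The forms in Appendix C ask the two items as follows.
- **Baseline, item 4a:** no filter ("The following questions are about taking your child to the dentist for any reason").
- **2 weeks:** caregivers who visited, or who answer Question 1.1 with "No, but I have made an appointment with the dentist", go to item 1.5, where their form ends. Items 1.6a and 1.6b come under "If you answered NO, and I have not made an appointment to Question 1.1 above, please answer the following questions".
- **Exit:** the filter is "4.5 Did your child visit the dentist after the school dental screening". A yes leads to section 5A, which has no want or plan item. The items appear only in 5B, for those answering no "to Question 4.5 (your child did not visit the dentist), please answer the following questions".
- **Spanish forms:** the same filters, "Si contestó NO, y no he hecho una cita a la Pregunta 1.1 de arriba, por favor responda a las siguientes preguntas" at 2 weeks, and at exit "Visitó su niño/a al dentista después de la evaluación dental en la escuela" followed by 5B, tied to a no "a la Pregunta 4.5 (su niño/a no visitó al dentista), por favor responda a las siguientes preguntas".

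Section 12.4 compares mean responses across arms by linear regression. If missing responses pass a missingness check, it uses available data with weights. Otherwise it uses multiple imputation from other item responses. It also makes intention the middle link of the mediation path, splits the effect into four paths, and treats 2 weeks as the time of greatest expected impact.

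**The concern.** Having visited a dentist or booked an appointment is a post-randomisation event that the letters are meant to cause. If the letters work, the arms differ in how many caregivers are asked about intention and in which ones. The text supplied gives no score for caregivers routed past the items.

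At stake are one secondary outcome and the explanation of how the letters work. A letter that raised attendance could appear to have lowered intention, or to have left it unchanged, purely because of who was asked. Intention is also unmeasured in the early actors, in whom the letter may have worked fastest.

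**Working it through.** **1. Planning rates.** Section 12.2 assumes 19% (standard letter, Arm 5), 37% (CSM letter, Arm 1) and 57% (CSM letter plus DIG, Arm 2). With its two-sided pooled Z test at 0.05, power at 204 per arm is 98.4% for 19% v 37% and 98.3% for 37% v 57%, which agrees with the stated 98%. The plan gives no power for intention.

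**2. Who would be asked.** Taking these as action rates, 204 × 0.81 = 165 in Arm 5, 204 × 0.63 = 129 in Arm 1 and 204 × 0.43 = 88 in Arm 2, before ordinary non-response.

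**3. Model (assumed).** Baseline intention, follow-up intention and propensity to act are jointly normal with unit SD, and there is no true arm effect on intention. Let r = correlation of follow-up intention with acting, b = correlation of baseline intention with acting, and c = correlation of baseline with follow-up intention (0.5). A caregiver acts when propensity exceeds the threshold z for rate p. Mean propensity among those asked is m(p) = -φ(z)/(1-p):
- m(0.19) = -0.335, m(0.37) = -0.599, m(0.57) = -0.913
- Arm 2 minus Arm 5: -0.578. Arm 1 minus Arm 5: -0.264.

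**4. Available data, raw score.** Bias = r × difference in m.

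| r | Arm 2 v 5 (SD) | Wrong-direction rejection, 165 v 88 | Arm 1 v 5 (SD) |
|---|---|---|---|
| 0.2 | -0.12 | 14% | -0.05 |
| 0.3 | -0.17 | 27% | -0.08 |
| 0.5 | -0.29 | 66% | -0.13 |

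The nominal wrong-direction rate is 2.5%. These are pairwise tests, whereas 12.4 specifies a three-group F-test followed by pairwise intervals.

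**5. Available data, change score (the outcome in 3.2.2).** Bias = (r - b) × -0.578 for Arm 2 v Arm 5.
- r = 0.5, b = 0.2: -0.17 SD, 27% wrong-direction
- r = 0.3, b = 0.2: -0.06 SD, 6%
- r = b: zero, 2.5%
- r = 0.3, b = 0.5: +0.12 SD, so the sign reverses

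**6. Imputation.** Baseline is complete and only follow-up is filled in, so the cancellation in step 5 is lost. Imputing from arm and baseline intention alone, with r = 0.5 and b = 0.2 to 0.5, leaves -0.24 to -0.17 SD in level and in change. Section 12.4 would use other items too. Suppose one more item is added that correlates 0.5 to 0.7 with follow-up intention, 0.3 to 0.5 with acting and 0.4 with baseline intention (all assumed). The remaining bias is then -0.19 to -0.10 SD at b = 0.2 and -0.14 to -0.05 SD at b = 0.5.

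**7. Two weeks.** If a share f of eventual actors, those with the highest propensity, have acted by then, the rates become 0.19f and 0.57f. At r = 0.5 the raw bias is 0.5 × [m(0.285) - m(0.095)] = -0.14 SD for f = 0.5, and -0.08 SD for f = 0.25. This leaves out appointment-holders who never attend.

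**8. Mediation.** Separating the four paths needs a model for care receipt given intention. At 2 weeks intention is observed only in those who have not yet acted. The limitation therefore reaches the separation of the direct and perception-alone paths as well as the paths through intention.

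**The case against.** Several points on the other side stand.
- **No document gives r or b.** The rejection rates depend on them, and for the change score the bias may be small or nil.
- **The rates do not match the filters.** The 57% counts appointments, so it overstates the exit filter, which is a visit only. The 19% came from a dental exam, not caregiver report.
- **The available-data branch may never be used.** The check in 12.4 asks whether missingness depends on other item responses. If Question 1.1 or 4.5 is among the items tested, the check must fail and imputation follows. Section 12.4 does not name the items.
- **Imputation has more to work with than baseline intention.** Item 2e (intending at least one dental visit a year) is asked of everyone at baseline and exit, and the IPQ-RD is not filtered. But 2e is not the defined outcome, it is absent from the 2-week form, and on the assumptions above it shrinks the bias without removing it.
- **The SAP is held separately** (Supplemental Materials) and may contain a scoring rule.

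The weighting in 12.4 does not help. Both items are skipped together, so a routed caregiver has no summary score to weight.

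A reader might infer that the trial should expect a false fall in intention about two times in three. The documents do not support that: the 66% belongs to the raw score, r = 0.5 and the widest rate gap. Nor do they support an inference that the effectiveness result is compromised, since care receipt is determined by dental exam.

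**Conclusion.** The forms cannot deliver the outcome that 3.2.2 defines for any caregiver who has acted, in either language, and neither branch of 12.4 restores a comparison of the randomised groups. That follows from the routing alone.

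The size does not. It rests on a normal model, assumed correlations and planning rates used as action rates. For Arm 2 v Arm 5 it runs from -0.12 to -0.29 SD for the raw score over r = 0.2 to 0.5. For the change score it runs from -0.17 SD through zero to a reversed sign.

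The arm comparison of intention is affected, as is every mediation component that conditions on intention. The total effect on care receipt, the primary and gatekeeping tests and the IPQ-RD arm comparison are not. This should be fixed, as a secondary-outcome and mechanism issue.

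**What to change.** **Caregivers not yet followed.** Move the want and plan items ahead of Question 1.1 (2-week form) and Question 4.5 (final form), in English and Spanish, so that everyone answers.

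**Caregivers followed on the current forms.**
- Do not present intention differences between arms as randomised comparisons.
- Analyse all who return the form with a pre-specified intention-or-action score that ranks action (visit or appointment at 2 weeks, visit at exit) above any intention score. Label it a different estimand that at exit overlaps with care receipt.
- Add a sensitivity analysis over a range of assumed scores for routed caregivers, with item 2e as an auxiliary variable at exit.

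**Mediation.** Report the decomposition involving 2-week intention as conditional on not having acted by 2 weeks.

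**Limits to state.** Section 5.3 still needs 258 caregivers, all from the second-year Ohio recruitment. Revised forms would therefore reach mainly about 258 of 660 (39%), and form version is confounded with site and year. For the other 660 - 258 = 402 or so, the missing scores cannot be recovered if they were followed on the current forms. Intention recorded after acting cannot mediate that action.

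If the separately held SAP already has a rule for routed caregivers, bring it into 12.4.

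**Cost.** Reordering two items on two forms in two languages, IRB approval and a little more analysis. No added visits or participants.
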